7.5 Data Pooling

Data will be pooled from all trial sites. The basis for pooling is the clinical basis described in Meinert^{xli} based on three critical features: all sites used the same protocol, the Sponsor monitored the sites to assure protocol compliance, and the sites all used the same data gathering mechanism (CRFs and data entry methods).

7.6 Assessment of Feasibility

7.6.1 Primary Feasibility Endpoint

Proportion of subjects that achieve procedural success. Procedural success is defined as the creation of an electrically isolating "box" lesion encompassing the pulmonary veins and posterior left atrium using the study device. Specifically, the ability of the device to create a contiguous line of electrical block in the specified region of the left atrium.

7.6.2 Secondary Feasibility Endpoint

The secondary feasibility endpoint(s) include:

Proportion of subjects that achieve long-term technical success. Long-term technical success is defined as electrical isolation of the pulmonary veins and posterior left atrium assessed at a follow-up electro-anatomical remapping procedure performed 3-months post index procedure.

7.7 Assessment of Safety

7.7.1 Primary Safety Endpoint

A composite safety endpoint consisting of the proportion of subjects that experience one or more of the following serious adverse events (SAEs) related to the investigational procedure and/or device within 30 days of the PEF ablation procedure or hospital discharge, whichever is later, except as noted below:

- Cardiac death
- Stroke and/or transient ischemic attack (TIA)
- Myocardial infarction (MI)
- Excessive bleeding or
- Atrio-esophageal fistula
- Persistent post-surgical phrenic nerve paralysis at 12 months
- Severe pulmonary vein stenosis

All adverse events (AEs) will be adjudicated for seriousness as well as device and procedure relatedness.

7.7.2 Secondary Safety Endpoint

The proportion of subjects reporting one or more SAEs for each follow-up interval. The intervals will include the period from:

- the surgical procedure for the surgical PEF ablation through the Day 30 follow-up visit;
- the Day 30 follow-up visit through the Month 3 follow-up visit;
- the Month 3 follow-up visit through the Month 6 follow-up visit; and

the Month 6 follow-up visit through the Month 12 follow-up visit.

7.8 Final Clinical Report

A final clinical report will be prepared at the conclusion of the trial. Copies of the final report will be provided to each investigator and to the respective IRBs/ECs.

8. Adverse Events and Serious Adverse Events

8.1 General

Adverse Event (AE):

Any untoward medical occurrence, unintended disease or injury, or untoward clinical signs (including abnormal laboratory findings) in subjects, users or other persons, whether or not related to the investigational medical device

NOTE 1: This definition includes events related to the investigational medical device or the comparator.

NOTE 2: This definition includes events related to the procedures involved.

NOTE 3: For users or other persons, this definition is restricted to events related to investigational medical devices.

Serious Adverse Event (SAE):

- led to death.
- led to serious deterioration in the health of the subject, that either resulted in
 - o a life-threatening illness or injury, or
 - o a permanent impairment of a body structure or a body function, or
 - o in-patient or prolonged hospitalization, or
 - medical or surgical intervention to prevent life-threatening illness or injury or permanent impairment to a body structure or a body function,
 - led to fetal distress, fetal death or a congenital abnormality or birth defect

NOTE: Planned hospitalization for a pre-existing condition, or a procedure required by the CIP, without serious deterioration in health, is not considered a serious adverse event.

Adverse Device Effect (ADE):

Adverse event related to the use of an investigational medical device

NOTE 1: This definition includes adverse events resulting from insufficient or **CONFIDENTIAL**

inadequate instructions for use, deployment, implantation, installation, or operation, or any malfunction of the investigational medical device.

NOTE 2: This definition includes any event resulting from use error or from intentional misuse of the investigational medical device

Serious Adverse Device Effect (SADE):

Adverse device effect that has resulted in any of the consequences characteristic of a serious adverse event

Unanticipated Serious Adverse Device Effect (USADE):

Serious adverse device effect which by its nature, incidence, severity or outcome has not been identified in the current version of the risk analysis report.

NOTE: Anticipated serious adverse device effect (ASADE) is an effect which by its nature, incidence, severity or outcome has been identified in the risk analysis report.

Device Deficiency:

Inadequacy of an investigational medical device related to its identity, quality, durability, reliability, safety or performance. This may include malfunctions, use error, or inadequacy in the information supplied by the manufacturer.

Use error:

Act or omission of an act that results in a different medical device response than intended by the manufacturer or expected by the user

NOTE 1: Use error includes slips, lapses, and mistakes.

NOTE 2: An unexpected physiological response of the subject does not in itself constitute a use error.

Malfunction:

Failure of an investigational medical device to perform in accordance with its intended purpose when used in accordance with the instructions for use or CIP.

Causality relationship:

The investigator will assess the causality of all adverse events in relation to the research, i.e., the relationship between the AE / SAE and the investigational device or any other study-related procedures.

Each SAE will be classified according to five different levels of causality:

CONFIDENTIAL

- 1) Not related: relationship to the device or procedures can be excluded when:
 - the event is not a known side effect of the product category the device belongs to or of similar devices and procedures;
 - the event has no temporal relationship with the use of the investigational device or the procedures;
 - the serious event does not follow a known response pattern to the medical device (if the response pattern is previously known) and is biologically implausible;
 - the discontinuation of medical device application or the reduction of the level of activation/exposure - when clinically feasible – and reintroduction of its use (or increase of the level of activation/exposure), do not impact on the serious event:
 - the event involves a body-site or an organ not expected to be affected by the device or procedure;
 - the serious event can be attributed to another cause (e.g. an underlying or concurrent illness/ clinical condition, an effect of another device, drug, treatment or other risk factors);
 - harms to the subject are not clearly due to use error;
 - In order to establish the non-relatedness, not all the criteria listed above might be met at the same time, depending on the type of device/procedures and the serious event.
- 2) Unlikely: the relationship with the use of the device seems not relevant and/or the event can be reasonably explained by another cause, but additional information may be obtained.
- 3) Possible: the relationship with the use of the investigational device is weak but cannot be ruled out completely. Alternative causes are also possible (e.g. an underlying or concurrent illness/ clinical condition or/and an effect of another device, drug or treatment). Cases were relatedness cannot be assessed or no information has been obtained should also be classified as possible.
- 4) Probable: the relationship with the use of the investigational device seems relevant and/or the event cannot reasonably have explained by another cause, but additional information may be obtained.
- 5) Causal relationship: the serious event is associated with the investigational device or with procedures beyond reasonable doubt when:
 - the event is a known side effect of the product category the device belongs to or of similar devices and procedures;
 - the event has a temporal relationship with investigational device use/application or procedures;
 - the event involves a body-site or organ that
 - the investigational device or procedures are applied to;

- the investigational device or procedures have an effect on;
- the serious event follows a known response pattern to the medical device (if the response pattern is previously known);
- the discontinuation of medical device application (or reduction of the level of activation/exposure) and reintroduction of its use (or increase of the level of activation/exposure), impact on the serious event (when clinically feasible);
- other possible causes (e.g. an underlying or concurrent illness/ clinical condition or/and an effect of another device, drug or treatment) have been adequately ruled out;
- harm to the subject is due to error in use;
- In order to establish the relatedness, not all the criteria listed above might be met at the same time, depending on the type of device/procedures and the serious event.

If an SAE is determined to be probably or definitely related to the device and has not been previously anticipated, the clinical finding would be classified as an unanticipated adverse device effect (UADE). An UADE is defined as "any serious adverse effect on health or safety or any life-threatening problem or death caused by, or associated with, a device, if that effect, problem, or death was not previously identified in nature, severity, or degree of incidence in the investigational plan or application (including a supplementary plan or application), or any other unanticipated serious problem associated with a device that relates to the rights, safety, or welfare of subjects."

8.2 Adverse Event Reporting

All AEs, including all SAEs, will be monitored from the time of enrollment through discharge for this trial. All AEs must be recorded in the patient chart and Case Report Form (CRF). A description of the event, including the start date, resolution date, action taken and the outcome should be provided along with the Investigator's assessment of the relationship between the AE and the trial device.

All AEs should be followed until the event is resolved or judged to be chronically stable. The investigational site will provide relevant follow-up information to the Sponsor upon request.

The investigator should report to the Sponsor or its designee the following events, whether expected or not, in the corresponding sheet of the CRF, with the exception of AEs / SAEs detected before the patients has signed the patient consent form.

- AE
- SAF
- Device Deficiencies that did not but might have led to a SAE if:
 - Suitable action has not been taken or

- Intervention had not been made or
- If circumstances had been less fortunate
- New findings/updated in relation to already reported events.

If an AE / SAE is present at the beginning of study prior to the subject providing signed consent to participate in the study, only its worsening should be reported.

The investigator shall notify the sponsor and the CRO immediately and not later than 24 hours after the investigator has become aware of a SAE or device deficiency that might have led to a SAE via the Adverse Event Form of the CRF.

This reporting should be done by faxing completed CRF pages to the CRO:

CRO: MedPass International SAS

[contact]

Sponsor: FARAPULSE, Inc. [contact]

Email: [contact]
Contact: [name]

In the case of a SADE, when possible, the device involved in the failure or malfunction is to be returned to the Sponsor for analysis.

8.3 Reporting to Ethics committee / Competent Authority

Depending on the local requirements or following agreement between both parties, the sponsor, its designated representative or the principal investigator will be responsible for performing safety reporting to the Ethics Committee according to the relevant local regulatory requirements.

The sponsor or designated representative will be responsible for reporting to the National Competent Authority according to national requirements and in line with MEDDEV 2.7/3.

9. Monitoring

9.1 Trial Monitoring

Clinical monitors, qualified by training and experience, will be responsible for monitoring and overseeing the conduct of the trial. The clinical monitors will evaluate compliance with the protocol, any specific recommendations made by the site's Ethics Committee (EC) and the signed Investigator Agreement. Phone contacts and site visits will be conducted to ensure that the protocol is being followed and that any protocol deviations are properly documented. Clinical monitoring will include a verification that Informed Consent Form was

properly obtained for all enrolled trial participants, a review of clinical records for accuracy and completeness, resolution of missing or inconsistent results and a review of source documents. The clinical monitor will verify that the Case Report Forms (CRFs) are in agreement with the source documentation and other records. The investigator will make available to the clinical monitor for review all Informed Consent documents, all completed CRFs, source documentation and other relevant records for all enrolled subjects at the site. It is important that the investigator and other relevant site personnel are available for consultation with the clinical monitors during the monitoring visits and that sufficient time is devoted at the site for the monitoring process.

If a deficiency is noted during an on-site visit or at any other time during the course of the trial, the clinical monitor is required to discuss the situation with the investigator and the Sponsor to ensure compliance.

The Sponsor or its designated representative, qualified by training and experience, will be responsible for monitoring and overseeing the conduct of the trial. The accuracy of all collected data will be verified for:

- Eligibility criteria
- Baseline characteristics
- Primary safety and feasibility endpoints
- Adverse events
- Secondary endpoints

with source documents including, but not limited to, medical records, office/clinic notes, procedure reports, laboratory results, physician and nursing progress notes. Verification and quality of data, monitoring of clinical study progress and Investigator compliance with the approved protocol will be conducted by the Sponsor or its designated representative.

The Sponsor or its designated representative must be allowed to visit the clinical site and have direct access to all study records throughout the duration of the study. The monitor will review all source data and compare them to the data documented in the case report forms, in addition to performing a review of the Regulatory Binder, and conducting device accountability. The Investigator and/ or institution will provide direct access to source data/ documents for trial-related monitoring, audits, and regulatory review and inspection.

It is important that the Investigator and relevant study personnel are available during the monitoring visits and that sufficient time is devoted to the process.

Additionally, telephone, email contact, and onsite visits will be conducted on a regular basis with the Investigator and the site staff to ensure that the protocol is being followed and to address any issues that may occur during the trial.

If a deficiency is noted during the course of the trial the clinical monitor is required to discuss the situation with the site and the Sponsor (if required) to secure compliance.

10. Study Management

The Sponsor has overall responsibility for the conduct of the study according to Good Clinical Practice Guidelines (ICH E6 Consolidated Guidance to Good Clinical Practice) as well as any conditions imposed by local and national regulatory authorities.

For this study, Sponsor will have direct responsibilities and will delegate other responsibilities to appropriate and qualified consultants, contractors and/ or Contract Research Organizations (CROs). Together, the Sponsor, consultants and CROs will ensure that the study is conducted according to the Clinical Investigational Plan and all applicable and governing regulations. All personnel to participate in the conduct of this clinical trial will be qualified by education and/ or experience to perform their tasks.

10.1.3 Clinical Sites

A complete listing of all clinical sites will be maintained by the Sponsor and will be available upon request.

10.2 Ethical Considerations

It is expected that all parties will share in the responsibility for ethical conduct in accordance with their respective roles in the investigation. The Sponsor and the Investigator(s) shall avoid improper influence or inducement of the subject, monitor, the clinical investigator(s) or other parties participating in or contributing to the clinical investigation.

10.2.1 Trial Conduct

The trial will be performed in accordance with the relevant parts of the

Code of Federal Regulations, ICH Guidelines for Good Clinical Practices, the European Standard ISO 14155, the Declaration of Helsinki, and any regional and/or national regulations. The clinical investigation shall not begin until the required approval has been obtained from the relevant national regulatory authority and the local Ethical Committee. Any additional requirements imposed by the regulatory authority or EC shall be followed. These principles shall prevail over interests of science and society and shall be understood, observed and applied at every step in this clinical investigation.

10.2.2 Ethics Review

Before any subject can be enrolled in this trial, the IRB or EC for the specific institution must review and approve the protocol and the Informed Consent Form to be used. A subject cannot be asked to sign the Informed Consent Form until the trial has been fully approved by the institution's Ethics Committee. The Sponsor or their designated CRO (MedPass International) will require a copy of any Ethics Committee correspondence, as well as the final Ethics Committee approval letter and the final Ethics Committee approvals for protocol and ICF revisions on amendments from each Ethics Committee.

10.2.3 Informed Consent

Subjects cannot be asked to sign the Informed Consent document until the trial has been fully approved by the respective institution's Ethics Committee and the Sponsor or their CRO representative. has received and reviewed the specific Ethics Committee-approved Informed Consent Form. When the investigator has determined the eligibility of a specific subject to enter the trial, the Informed Consent Form must be completed. The consent form must be read and understood by the subject, the subject's questions answered and the form signed by the subject before any study-related procedures can be performed. All subjects are to receive copies of their signed Informed Consent Form.

10.2.4 Coverage of Expenses

Study participants will be reimbursed for travel costs related to study hospital visits.

10.2.5 Confidentiality

Confidentiality of subjects will be maintained throughout the trial. A unique identification code will be assigned to each subject participating in this trial. Any data that may be published in abstracts, scientific journals, or presented at medical meetings will reference a unique subject code and will not reveal the subject's identity. The Sponsor and their CRO representative will make every reasonable effort to protect the confidentiality of all subjects participating in the trial.

10.3 Insurance

The Sponsor will maintain the appropriate and necessary insurance coverage for the duration of the study.

10.4 Audits and Inspections

The principal investigator will also allow representatives of the governing EC, Competent Authority (CA), the U.S. Food and Drug Administration (FDA), and other applicable regulatory agencies to inspect all study records, CRFs, and corresponding portions of the subject's office and/or hospital medical records at regular intervals throughout the trial. These inspections are for the purpose of verifying adherence to the protocol, completeness and exactness of the data being entered onto the CRFs and compliance with FDA or other regulatory agency regulations.

The principal investigator will inform the Sponsor or the Sponsor's designee should they be audited or inspected by any regulatory agencies. The Sponsor or the Sponsor's designee will also inform the site if they are made aware of a pending audit or inspection by a regulatory agency.

10.5 Study Suspension or Early Termination

The study can be discontinued at the discretion of the Investigator or study Sponsor for reasons including, but not limited to, the following:

- Occurrence of adverse events unknown to date in respect to their nature, severity, or duration, or the unexpected incidence of known adverse events
- Obtaining new scientific knowledge that shows that the study is no longer valid or necessary
- Data demonstrates a benefit to subjects who undergo ablation for atrial fibrillation with the FARAPULSE Cardiac Ablation System making treatment without the FARAPULSE Cardiac Ablation System unethical
- Insufficient recruitment of subjects
- Unanticipated adverse device effect (UADE) presenting an unreasonable risk to subjects (Sponsor may terminate the study immediately)
- Persistent non-compliance with the protocol
- Persistent non-compliance with regulatory requirements

If the study is discontinued or suspended prematurely, the Sponsor shall promptly inform all clinical investigator(s)/ investigational center(s) of the termination or suspension and the reason(s) for this. The national and local regulatory authorities shall also be informed promptly and provided with the reason(s) for the termination or suspension by the Sponsor or by the clinical investigator/ investigation center(s).

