4.6 Return of Devices

All unused investigational devices will be returned to the study Sponsor upon completion of the clinical study. All used investigational devices will be returned to the study Sponsor for analysis. Any investigational device that fails to perform correctly will be equally returned to the study Sponsor for analysis. The Investigator or his/ her designated representative is responsible for device accountability and disposition of all used and unused devices. The study Sponsor or its designated representative will conduct device reconciliation at the completion of subject enrollment or at the conclusion of the study.

5. Trial Objectives

The objective of this feasibility and safety trial is to demonstrate that the creation of electrically isolating lesions generated by pulsed electric field ablation using the FARAPULSE Cardiac Ablation System during concomitant heart surgery is feasible and a safe treatment for paroxysmal atrial fibrillation.

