5.3 Trial Design

5.3.1 Description of Trial Design

Prospective, single-arm, multi-center feasibility trial. Subjects will be consented to undergo surgical PEF ablation using the FARAPULSE Cardiac Ablation System concomitant to heart surgery. Subjects will be followed at 30 days, 3 months, 6 months and 12 months following the index surgical procedure with a blanking period for recurrent atrial fibrillation or atrial tachycardia of 3 months following the index surgical procedure.

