7.1 General Statistical Considerations

The primary objective of this study is to characterize the safety and feasibility of the FARAPULSE Cardiac Ablation System in subjects with paroxysmal atrial fibrillation undergoing cardiac surgery.

The study is a feasibility study with no formal hypothesis testing and therefore no required sample size. Study results will be presented using descriptive statistics. Results from this study will be used to design additional clinical studies.

All subjects will be followed on an intent-to-treat basis. The device performance will be assessed based on a per-protocol analysis of the primary safety and feasibility endpoints and secondary efficacy endpoints. An intent-to-treat analysis, along with other secondary analyses, will also be completed and reported.

Demographic, baseline clinical and disease characteristics, procedural results and primary, secondary and all additional endpoints will be summarized using descriptive statistics.

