10.14 Study Suspension or Early Termination

The study can be discontinued at the discretion of the Investigator or study Sponsor for reasons including, but not limited to, the following:

- Occurrence of adverse events unknown to date in respect to their nature, severity, or duration, or the unexpected incidence of known adverse events
- Obtaining new scientific knowledge that shows that the study is no longer valid or necessary
- Data demonstrates a benefit to subjects who undergo cardiac surgery with the FARAPULSE Cardiac Ablation System making treatment without the FARAPULSE Cardiac Ablation System unethical
- Insufficient recruitment of subjects
- Unanticipated adverse device effect (UADE) presenting an unreasonable risk to subjects (Sponsor may terminate the study immediately)
- Persistent non-compliance with the protocol
- Persistent non-compliance with regulatory requirements

If the study is discontinued or suspended prematurely, the Sponsor shall promptly inform all clinical investigator(s)/ investigational center(s) of the termination or suspension and the reason(s) for this. The national and local regulatory authorities shall also be informed promptly and provided with the reason(s) for the termination or suspension by the Sponsor or by the clinical investigator/ investigation center(s).

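### Sections 10.5 and 10.14 allow the study to be stopped because its data show a benefit over treatment without the device, which a single-arm descriptive study cannot show

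*Combined protocol and SAP*

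**What the plan says.** Sections 10.5 and 10.14 both carry the title Study Suspension or Early Termination and are near duplicates. Each opens by saying that "The study can be discontinued at the discretion of the Investigator or study Sponsor for reasons including, but not limited to, the following". One listed reason in 10.5 is "Data demonstrates a benefit to subjects who undergo ablation for atrial fibrillation with the FARAPULSE Cardiac Ablation System making treatment without" the device unethical. The matching reason in 10.14 begins "Data demonstrates a benefit to subjects who undergo cardiac surgery with the FARAPULSE Cardiac Ablation System" and ends the same way.

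The design sections describe a study of another kind. Section 5.3.1 calls it a "Prospective, single-arm, multi-center feasibility trial". Section 7.1 says "The study is a feasibility study with no formal hypothesis testing and therefore no required sample size" and "Study results will be presented using descriptive statistics". Sections 5.5 and 7.2 set enrolment at up to 25 subjects, with no minimum. Section 7.2 calls the trial first-in-man and leaves efficacy to later, fully powered studies. Section 10.12 gives the Clinical Events Committee power to pause or terminate, on safety grounds only.

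The aim is worded in two ways. Section 5 says "The objective of this feasibility and safety trial is to demonstrate that the creation of electrically isolating lesions" by this method is feasible and safe, and the synopsis objective uses the same verb. Section 7.1 says the primary objective is to *characterize* safety and feasibility. The synopsis hypothesis asserts outright that the treatment is feasible and safe.

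**The concern.** To say that treatment without the device has become unethical is to compare outcomes with and without it. The trial observes outcomes only with it. No endpoint, threshold, timing or independent body is attached to the judgement of benefit. If the bullet were ever used, it would be because uncontrolled results looked good at a moment that the sponsor or an investigator chose.

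Two things are at stake. A stop on a good run biases the reported success proportion upward, and 7.1 says the results will be used to design further studies. It also shortens the safety record of a first-in-man device. A stop during accrual means fewer treated subjects. A stop afterwards could mean incomplete follow-up, and persistent phrenic nerve paralysis, a component of the primary safety endpoint (5.4.1), can only be established at 12 months.

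**Working it through.** The plan has no stopping boundary, power or performance goal to reproduce. The check therefore has three parts: whether the bullet can be triggered validly, what a stop on favourable results would cost, and whether the objective is worded in keeping with the design.

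**1. Can the bullet be triggered validly?** It needs a comparator, a criterion for benefit, and someone charged with applying it. Section 5.3.1 supplies no comparator. Section 7.1 supplies no test and section 7 gives no study-level threshold. Section 10.12 limits the committee to safety. All three are missing, and no other section supplies them. Even a perfect result is only a within-arm estimate: 25/25 successes has an exact 95% interval of 86.3% to 100%, and 10/10 has 69.2% to 100%.

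**2a. Bias in the success proportion.** Inputs from the plan: a maximum of 25 subjects (5.5), and a primary feasibility endpoint known from the procedural maps (5.4.3, 5.13.2). Assumed: a look after each subject from the 10th, a stop at 95% or more observed success, and a true success rate p of 80% or 90%.

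Under this rule a stop can occur at only two points: at 10/10, or at 19/20 with the single failure among the first ten. Two failures would need 38/40.

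- P(stop at 10) = p^10
- P(stop at 20) = 10(1−p)p^19
- Mean size = 25 − 15·P(stop at 10) − 5·P(stop at 20)
- Bias = P(stop at 10)·[1 − (10+15p)/25] + P(stop at 20)·[0.95 − (19+5p)/25]

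| | p = 90% | p = 80% |
|---|---|---|
| P(stop at 10) | 0.349 | 0.107 |
| P(stop at 20) | 0.135 | 0.029 |
| P(early stop) | 0.484 | 0.136 |
| Mean size | 19.1 | 23.2 |
| Bias | 0.349×0.06 + 0.135×0.01 = 0.022 | 0.107×0.12 + 0.029×0.03 = 0.014 |
| Mean reported rate | 92.2% | 81.4% |

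A looser assumed trigger, 90% or more observed success, gives these results by exact recursion:

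| True rate | Mean reported, looks from 5th | Mean reported, looks from 10th |
|---|---|---|
| 60% | 62.9% | 60.9% |
| 70% | 74.8% | 72.0% |
| 80% | 86.1% | 83.0% |

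The bias is therefore about 3 to 6 points with looks from the 5th subject and about 1 to 3 points with looks from the 10th.

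**2b. Safety precision.** With zero events in n subjects, the exact two-sided 95% upper limit is 1 − 0.025^(1/n).

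| n | Upper limit |
|---|---|
| 25 | 13.7% |
| 23 | 14.8% |
| 19 | 17.6% |
| 10 | 30.8% |

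The rows for 23 and 19 are close to the mean sizes above. The row for 10 is the earliest stop that the assumed rule allows. A true event rate of 10% would show no events with probability 0.9^10 = 35% at n = 10, against 0.9^25 = 7% at n = 25.

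**2c. Timing.** Enrolment is estimated at 6 months (synopsis), while therapeutic success runs to Month 12 (5.4.5). On that estimate no 12-month outcome exists during accrual. A stop then would rest on acute procedural success and some 3-month remaps. A later stop could cost follow-up rather than subjects.

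**3. The objective.** Event-free results in all 25 subjects would occur with probability 7% at a true event rate of 10%, and 0.95^25 = 28% at a true rate of 5%. The design can describe safety, as 7.1 says; it cannot *demonstrate* it.

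**The case against.** The best defence is that the bullet does almost nothing. Read literally it sets a bar that this trial can never meet. The discretion to stop exists without it, because the list is expressly not exhaustive and enrolment has no minimum. The trigger modelled above is not in the protocol. It uses a lesion outcome, while the patient-level outcome is therapeutic success, listed only as an additional observation. A stop would also be visible: 10.5 and 10.14 require that the reasons be given to investigators and authorities, and 10.16 requires a final report even after premature termination. Larger studies follow in any case.

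Most of this stands, and it limits the size of the point. It does not rescue the bullet. A reason that cannot validly arise has no proper use, and listing it lends protocol authority to a stop on favourable results. The objection does show that deletion alone is not enough.

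Two stronger readings are tempting. A reader might infer that the plan inflates a false-positive rate, but 7.1 plans no test, so there is no type I error to inflate. A reader might also infer that 10.5 and 10.14 name different populations. They do not: every subject has ablation for atrial fibrillation during cardiac surgery, so the mismatch is editorial.

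**Conclusion.** The point holds as a should-fix item of modest size. The bullet asks for a comparative conclusion that the design cannot give, and its only practical use is to justify stopping on favourable uncontrolled results.

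A reader might infer that the success rate would be badly distorted. The figures do not support that: about +1 to +2 points under the stricter assumed trigger and at most about +6 under the looser ones. The larger cost is the zero-event upper limit, which rises from 13.7% at full enrolment to about 17.6% at 19 subjects. The 30.8% at 10 subjects is an extreme case, not the expected one. Possible loss of 12-month data comes on top of this. The protocol does not say that follow-up would end with such a stop, so that loss is a risk and not a certainty.

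The bias and mean-size figures depend on assumed triggers, look times and true rates, because the plan gives none. The conclusion that the bullet cannot be validly triggered depends on none of them.

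**What to change.** - Delete the benefit bullet from 10.5 and from 10.14. This also removes the wording mismatch.
- Because the list is open-ended, add one sentence in both places: neither enrolment nor 12-month follow-up will be stopped early because of favourable results.
- Leave the safety, recruitment, compliance and new-knowledge reasons as they are. The new-knowledge reason already covers evidence that makes the study no longer valid or necessary.
- In the synopsis objective and section 5, replace *demonstrate* with *characterize*, to match 7.1. The synopsis hypothesis does not contain that verb, so reword it as a descriptive aim in place of an assertion that the treatment is feasible and safe.

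The cost is a few lines of text and a small loss of sponsor discretion. No extra subjects, visits or data are needed.
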